## 1 Introduction

The Canakinumab Anti-inflammatory Thrombosis Outcomes Study (CANTOS; Novartis study code CACZ885M2301) is a randomized, double-blind, placebo-controlled, event-driven trial of quarterly subcutaneous canakinumab in the prevention of recurrent cardiovascular events among stable post-myocardial infarction patients with elevated hsCRP.

This document outlines the agreements for the Statistical Analysis Plan for CANTOS based on the discussions between [REDACTED] and Novartis. The detailed statistical analysis plan including additional supportive [REDACTED], table shells and data set specifications will be prepared on this basis.

It is planned that after the end of the core study visit patients will be followed for safety in an extension study. Data collected after the end of the core study visit will not be part of the main CANTOS clinical database and analyses using data from this extension study will not be specified in this document.

## 2 Definitions

### 2.1 Analysis sets

The following analysis sets will be defined for statistical analysis:

- **Screened set** – All patients who signed the informed consent.
- **Randomized set** – All patients who received a randomization number, regardless of receiving trial medication.
- **Safety set (SAF)** – All patients who received at least one dose of study drug and have at least one post-baseline safety assessment. Of note, the statement that a patient had no adverse events also constitutes a safety assessment. Patients will be analyzed according to treatment received. Treatment received will be considered identical to the randomized treatment if the patient has during at least one visit received the two injections constituting the treatment assignment at randomization.

For patients who cannot be assigned in this manner, the most frequent dose at an individual visit (as defined in [table 2-1](#)) will be considered the treatment received. In the case of more than one equally frequent dose (ties), the highest most frequent dose will be assigned.

Note: Any patient who did not receive any injection of study drug during the study is automatically excluded from the safety set, due to the lack of at least one dose of study medication.

**Table 2-1 Definition of dose received at a visit**

Sum of injection doses* [mg]	Dose at the visit
0 (meaning $\geq 1$ placebo injections, but not even a partial canakinumab injection)	Placebo

Sum of injection doses* [mg]	Dose at the visit
> 0 to ≤ 50 mg of canakinumab	Canakinumab 50 mg
> 50 to ≤ 150 mg of canakinumab	Canakinumab 150 mg
> 150 of canakinumab	Canakinumab 300 mg

\* Placebo injections counted as 0 mg

- **Full analysis set (FAS)** – All randomized patients. This is the primary efficacy population applied in all efficacy variables. Following the intent-to-treat principle, patients are analyzed according to the treatment they have been assigned to at the randomization. However, patients who have not been qualified for randomization and who have been inadvertently randomized into the study are excluded from FAS, provided these patients have not received study drug. (Note: The last part of the definition of the FAS is what is often referred to as misrandomized patients; i.e. patients for whom IVRS calls were made by the site either prematurely or inappropriately prior to confirmation of the patient’s final randomization eligibility and double-blind medication was not administered to the patient. These patients would subsequently not continue to take part in the study or be followed-up. Misrandomized patients will not be included in the FAS, but they will be included in the Randomized Set. Further exclusions from the FAS may only be justified in exceptional circumstances; e.g., serious Good Clinical Practice violations).

**Per protocol set 1 (PPS1)** – a subset of the FAS, consists of all randomized patients in FAS who take at least one dose of study medication and have no major protocol deviations affecting the primary analyses. Major protocol deviations leading to exclusion from PPS will be specified prior to database lock on a blinded basis and documented in a separate document. Data from patients discontinuing treatment will be censored a quarter year + 28 days after their last study drug injection.

All cases of prospectively defined protocol deviations will be identified prior to clinical database lock / unblinding and entered into a dedicated data panel as part of the locked database. Certain deviations may stipulate that only data up to the time of infraction will be included in the PP analysis, i.e. for analyses of the PP set data beyond this time -point will be ignored. This supplemental efficacy population is used to assess robustness of the primary analysis results. All exceptional cases and problems and the final decisions on the allocation of patients to populations will be fully defined and documented before data base lock (in particular before breaking the blind where applicable) and will be fully identified and summarized in the clinical study report as per the harmonized International Conference on Harmonization of technical requirements for registration of pharmaceuticals for human use tripartite guideline on statistical principles for clinical trials.

Criteria defining protocol deviations are provided in the Data Handling Plan (DHP). Protocol deviations will not lead to patient withdrawal from the study unless they indicate a significant risk to the patient’s safety.

For the purpose of summarizing major protocol deviations, these will be considered to be those protocol deviations that lead to the exclusion from an analysis set. The current draft list of criteria leading to exclusions from analysis sets is shown in [Table 2.2](#). Other currently

foreseen protocol deviations will be reported in the clinical study report, but these will not lead to an exclusion from any analysis set. It is not currently foreseen that any criteria would lead to an exclusion from PPS from date of deviation.

**Table 2.2 Criteria leading to exclusions from analysis sets**

Analysis set	Criteria that cause a screened patient to be excluded
Screened	none
Safety (SAF)	Patients not receiving any dose of double-blind study medication
Randomized	Patient without a randomization number Patient was not randomized but took study drug (covered by the above)
Full Analysis Set (FAS)	Patient mis-randomized Patient without a randomization number Patient was not randomized but took study drug Site closed for GCP non-compliance (data integrity was impacted)
Per Protocol set 1 (PPS1)	Patient mis-randomized Patient without a randomization number Patient was not randomized but took study drug Patients not receiving any dose of double-blind study medication Patient participates in any other investigational drug or device study or patient has received an investigational drug or device <= 30days of Visit 1 except for previous DES trial on countries with approved DES devices Patient received study drug, and was later discontinued due to not meeting the entry criteria Major surgical procedure including PCI or CABG performed during the study but planned prior to randomization. CABG < 3 years prior to visit 1 Patient is currently (i.e. at randomization) taking a biological drug targeting the immune system (ie: TNF blockers, anakinra, rituximab, abatacept, tocilizumab) Documented MI does not meet entry criteria or Date of most recent MI = blank but there is a visit 2 Screening hsCRP < 2 mg/L or = blank Qualifying hsCRP measurement date < 28 days after date of prior PCI or Qualifying hsCRP measurement date < 28 days after date of qualifying MI
Exclusion of data from PPS from date onwards	Data from patients discontinuing treatment will be censored a quarter year + 28 days after their last study drug injection.

## 2.2 Subgroup definitions

Generally subgroup analyses within a trial should be kept to a minimum. However, subgroup analyses need to be presented in submission documents like Summary of Clinical Efficacy, Summary of Clinical Safety, and Risk Management Plan and the clinical study report for the CANTOS trial will likely at least fulfill the first two of these roles.

The objective of the subgroup analyses is to evaluate the consistency of treatment effects across a wide variety of patient groups.

The primary composite (MACE) endpoint of CV death, nonfatal MI and nonfatal stroke, the key secondary variables and potentially other important efficacy variables will be analyzed for the subgroups shown in the [Table 2.3-1](#).

**Table 2.3-1 Subgroup analyses for the primary major adverse cardiovascular event (MACE) endpoint and other key efficacy outcomes**

Subgroups	Definition
Age (at study start)	<65, ≥65 years ; <75, ≥75 years
Sex	male, female
Race	Asian, Black, Caucasian, Other
Ethnicity	Hispanic / Latino, Asian, Other, Unknown
Type of qualifying MI	STEMI, non-STEMI, unknown
BMI at baseline	< 25, ≥ 25 & < 30, ≥ 30 kg/m  ; < 35, ≥ 35 kg/m 
Region	
 
• Asia: China, India, Japan, South Korea, Taiwan
 
• Western Europe: Austria, Belgium, Germany, Greece, Iceland, Italy, Netherlands, Norway, Sweden, United Kingdom
 
• Central Europe: Bulgaria, Croatia, Czech Republic, Estonia, , Hungary, Latvia, Lithuania, Poland, Romania, Russian Federation, Serbia, Slovakia, Slovenia, Turkey
 
• Latin America: Argentina, Brazil, Colombia, Guatemala, Mexico, Peru
 
• North America: Canada, United States
 
• Others: Australia, South Africa
 
 
In addition to the above regions in all tables by region subgroup, an analysis for Japan (and Japan plus Korea) will also be presented separate regardless the size of enrollment in these countries to meet Japanese regulatory requests.

Glycemic status at baseline	
Normoglycemic, pre-diabetic, diabetic
 
Pre-diabetic is defined by one of the followings
 
 
• HbA1c ≥5.7% & <6.5%
 
• FPG ≥100 & <126 mg/dl
 
• FPG ≥ 126 mg/dl at either Visit 1 or Visit 2 (or any unscheduled visit between, but only occurring on one visit)
 
• HbA1c ≥ 6.5% at either Visit 1 or Visit 2 (or any unscheduled visit between, but only occurring on one visit)
 
 
Diabetic is defined by one of the followings
 
 
• FPG ≥ 126 mg/dl at Visit 1 and Visit 2 (or any unscheduled visit between)
 

Subgroups	Definition
	
 
HbA1c <math>\geq</math> 6.5% at Visit 1 and Visit 2 (or any unscheduled visit between)
 
Combination of FPG <math>\geq</math> 126 mg/dl and HbA1c <math>\geq</math> 6.5% as confirmed at Visit 1 and Visit 2 (or any unscheduled visit between)
 
Medical history of Type I or Type II diabetes mellitus
 
Anti-diabetic medication use
 

Smoking status at baseline	Never, current, former
Baseline hsCRP level	$\leq$ 4, $>$ 4 mg/L
Baseline LDL-C level	$<$ 70 mg/dL, $\geq$ 70 mg/dL; Tertiles of baseline LDL-C (This will be done using the calculated LDL-C unless triglycerides $>$ 400 mg/dL in which case a direct (i.e. measured) LDL-C will be used)
Baseline SBP level	$<$ 130 mmHg, $\geq$ 130 mmHg
Baseline DBP level	$<$ 80 mmHg, $\geq$ 80 mmHg
Baseline statin dose level	No, low, moderate, and high
Baseline aspirin usage/dose	Yes / No
Medical history of gout	Yes / No
Cardiovascular risk factors	
Hypertension	Yes / No
Dyslipidemia	Yes / No
Prior PCI	Yes / No
Prior CABG	Yes / No
Prior TIA/stroke	Yes / No
History of heart failure	Chronic Heart Failure occurrence (yes/no)
eGFR MDRD	$<$ 60, $\geq$ 60 & $<$ 90, $\geq$ 90 mL/min/1.73m 
Time since index MI	$<$ 6 vs. $\geq$ 6 months ; $<$ 12 vs. $\geq$ 12 months
Presence of MI prior to index MI	Yes / No

A set of standard safety subgroups shown in [Table 2.3-2](#) will by default be looked at for selected safety analyses (see [section 7](#)).

**Table 2.3-2 Standard safety subgroups**

Subgroup	Definition
Age	$<$ 65, $\geq$ 65 years; $<$ 75, $\geq$ 75 years
Sex	male, female

Subgroup	Definition
Race	The same as above
Ethnicity	The same as above
Region	The same as above
Time since index MI	< 6 months vs. ≥ 6 months
BMI	The same as above
Medical history of gout	Yes / No
Co-existing medical conditions of interest: T2DM	Yes / No
Baseline hsCRP level	The same as above

In addition to the two preceding sets of subgroups those specified in [Table 2.3-3](#) will be used in some analyses as stated in the relevant analysis plan sections. They are shown here irrespective of what kind of analysis they will be used for to highlight that they needed to be included in analysis datasets.

**Table 2.3-3 Additional subgroups needed only for specific analyses**

Subgroups	
Duration of diabetes	< 3, ≥ 3 & < 10, ≥ 10 years
Basis for diabetes diagnosis	
 
• Medical History of Type I or Type II diabetes mellitus
 
• Medical History and Anti-diabetic medication
 
• Medical History and Baseline HbA1c/FPG
 
• Medical History and Anti-diabetic medication and Baseline HbA1c/FPG
 
• Anti-diabetic medication
 
• Anti-diabetic medication and Baseline HbA1c/FPG
 
• Baseline HbA1c/FPG
 

Baseline HbA1c categories	
 
• HbA1c < 7% at randomization for deterioration of glycemic control analyses (HbA1c ≥ 7.5% at 6 month visit or beyond, confirmed by a second/unscheduled HbA1c measurement within 6 weeks) [i.e. Among those randomization diabetic patients, we look at the sub-group of patients with HbA1c < 7% at visit 2. Then we would analyze how many of those patients experience a deterioration of glycemic control as documented by an increase of HbA1c to ≥ 7.5% at 6 months or beyond, confirmed within 6 weeks.]
 
• For HbA1c benefit analysis in diabetics (HbA1c < 8%, ≥ 8%) [i.e. analysis of mean HbA1c change from baseline in T2D patients with baseline HbA1c < 8% and ≥ 8%.]
 

History of macular degeneration	Medical history or use of relevant medications
Baseline neutrophil levels	Abs neutrophils < 1.5 , ≥ 1.5 x 10  /L
Baseline use of antithrombotic medications	Yes/No
key drugs for the trial population affected by CYP450 with a narrow therapeutic index (e.g. warfarin and amiodarone)	Yes/No •
Vaccines	Yes/No
Medical history of gout, rheumatoid arthritis or other inflammatory diseases such as lupus or psoriatic arthritis	Yes/No
History of malignancy	Yes/No - Yes will correspond to patients with SMQ "Malignant or unspecified tumors" in Medical history
Baseline QTcF	Elevated or normal

Subgroups	
	Normal • ≤ 430 msec for men, ≤ 450 msec for women Elevated • > 430 msec for men, > 450 msec for women.
Baseline heart rate	< 55 bpm versus ≥ 55 bpm
Alcohol history	Yes / No
Baseline platelet counts	< 150, ≥ 150 x 10  /L
Early drops in platelet counts (or thrombocytopenia) Ordinal	< 25, ≥ 25 - <50, ≥ 50 - <75, ≥ 75 - < LLN, ≥ LLN at visit 3. Repeat at visit 4;
Early drops in platelet counts (or thrombocytopenia) defined by % change from baseline	< 20% and ≥ 20% drop from baseline to visit 3. Repeat at visit 4
Early drops in neutrophils (or neutropenia)	<0.5, ≥0.5 - <1.0, ≥1.0 - <1.5, ≥1.5 - <LLN at visit 3. Repeat at visit 4
Early drops in neutrophils (or neutropenia) defined by % change from baseline	< 20% and ≥ 20% drop from baseline to visit 3. Repeat at visit 4
baseline neutropenia	CTC ≥3 (yes/no)

To support regional submission activities and health authority interactions, at a minimum the subgroups shown in [table 2.3-4](#) are needed.

**Table 2.3-4 Regional/country subgroups to support regional/local submissions, for which selected tables have to be repeated**

Preliminary* list of variable(s) / analyses to be repeated	Regional/country subgroup
On FAS Disposition/Demography/Patient and disease characteristics Incidence of primary endpoint Incidence of key secondary endpoints Incidence of secondary endpoints (includes death) Analyses of other selected efficacy variables (e.g. hsCRP) Medical environment (e.g. prior/concomitant medications including statin dose, revascularization/stenting/etc. for index MI)	1. Japan 2. Japan and Korea 3. Mainland China 4. Mainland China + Taiwan 5. Asian patients: Japan, China, Taiwan, and Korea 6. India 7. Russia
On SAF Adverse events by system organ class and preferred term Serious adverse events by system organ class and preferred term Deaths Standardized MedDRA queries	

[figure not shown]
Preliminary* list of variable(s) / analyses to be repeated	Regional/country subgroup
Adverse events of special interest	

\* subject to changes dependent on local requirements

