5.2 Treatment arms

Following protocol Amendment 6 patients will be assigned to one of the following 4 treatment arms in a ratio of 1.4 : 1.3 : 1.3 : 2

- Canakinumab 50 mg s.c. at randomization (month 0), placebo s.c. at week 2 (month 0.5) , 50 mg s.c. at week 12 (month 3) and thereafter 50 mg s.c. quarterly
- Canakinumab 150 mg s.c. at randomization (month 0), placebo s.c. at week 2 (month 0.5), 150 mg s.c. at week 12 (month 3) and thereafter 150 mg s.c. quarterly
- Canakinumab 300 mg s.c. at randomization (month 0), week 2 (month 0.5) , week 12 (month 3) and thereafter 300 mg s.c. quarterly
- Placebo s.c. at randomization (month 0), week 2 (month 0.5) , week 12 (month 3) and thereafter placebo s.c. quarterly

with allocation in a 1.3 : 0.7 : 1 ratio to 300 mg, 150 mg and placebo respectively in randomization plan A and 0.6 : 1.4 : 1 to 150 mg, 50 mg and placebo respectively in randomization plan B. All patients will be equally likely to be assigned to randomization plan A or B. Within each of the two randomization plans patients will have a 2:1 probability of being on active treatment. Prior to protocol amendment 6, patients were assigned in a 1:1:1

ratio to the 300 mg arm, the 150 mg arm or placebo. Across trial parts 1 and 2 this will approximately result in a 1:1:1:1.5 allocation to 300, 150, 50 mg and placebo, respectively. More precisely, given about 743 patients in trial part one and 9257 in trial part 2, the overall patient allocation would be approximately 2253 for both the 300 and 150 mg groups, 2160 for the 50 mg group and 3333 for the placebo group (a 1.01:1.01:0.97:1.5 ratio).

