#### 7.4.5 Neutropenia

Drug effects on neutrophils will be assessed by the laboratory analyses described in [section 7.3.2](#), additionally decreased neutrophil counts (occurrence of neutropenia) per CTC grades as shown in [table 7-8](#) will be reported and baseline neutrophil / white blood cell counts will be taken into account in this analysis. Shifts versus baseline will also be shown per CTC grade.

Whether baseline neutropenia or early drops in neutrophil counts (or neutropenia) are indicative of infections (defined using adjudicated events of infection, investigator reported infections, and AEs of special interest) will be explored in two separate Cox regression models; one including treatment, baseline neutropenia and the interaction term as covariates, and the second model including treatment, early drops in neutrophil counts (or neutropenia) and the interaction term as a covariate. There are two definitions for the early drop in neutrophil counts (or neutropenia) subgroup, one using an ordinal variable and one using percentage change from baseline, and these are both computed at visits 3 and 4, see Table 2.3-3. There will therefore be four models for this endpoint and these will be displayed in the same table.

[figure not shown]

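### The ordinal early-neutrophil-drop variable has no level for normal counts, so two of the four early-drop infection models lack an unaffected reference group, and none of the four has a stated landmark

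*SAP*

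**What the plan says.** SAP Table 2.3-3 gives two definitions of an early drop in neutrophils. The ordinal one reads "<0.5, ≥0.5 - <1.0, ≥1.0 - <1.5, ≥1.5 - <LLN at visit 3. Repeat at visit 4". The percentage one reads "< 20% and ≥ 20% drop from baseline to visit 3. Repeat at visit 4". The corresponding ordinal platelet row in the same table ends "≥ 75 - < LLN, ≥ LLN at visit 3. Repeat at visit 4", so it does provide for a normal count.

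SAP 7.4.5 asks whether baseline neutropenia or early drops point to later infection, and fits Cox models to find out. One model uses baseline neutropenia. The other is described as "the second model including treatment, early drops in neutrophil counts (or neutropenia) and the interaction term as a covariate". The section says there are two definitions of early drop, "one using an ordinal variable and one using percentage change from baseline, and these are both computed at visits 3 and 4", and concludes: "There will therefore be four models for this endpoint".

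Protocol Table 6-1 places Visit 3 at Month 1.5 and Visit 4 at Month 3. SAP 7.4.5 states no time origin for these models. The general Cox model for safety events in SAP 7.2 has no delayed entry, and SAP 7.3.1 includes adverse events with onset after randomization.

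**The concern.** A model that asks whether an early fall in neutrophils signals infection needs patients whose count did not fall below normal. The ordinal variable gives those patients no level. If it is programmed as listed, a normal count has no value and the patient leaves the model. What remains compares grades of neutropenia with one another. That remnant is also selected on a post-randomization count which treatment may affect, so its treatment and interaction terms would describe only patients who became neutropenic.

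The second issue is timing. The covariate is known only at Month 1.5 or Month 3. If the infection clock starts at randomization, an infection in week 3 counts as an outcome of a blood count taken weeks later. The order of cause and effect is then unclear, because an infection may itself move the count. This applies to all four early-drop models.

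Neutropenia and infections are both listed safety topics (SAP Table 7-4). At stake is whether these models can answer the question that SAP 7.4.5 sets them.

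**Working it through.** **1. The plan's own count.** Two definitions × two visits = 4 early-drop models, as SAP 7.4.5 states. The ordinal definition accounts for 1 × 2 = 2 of them.

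**2. Are the ordinal levels exhaustive?** I assigned test counts (× 10⁹/L; the row gives no unit, but the cut-points match SAP Table 7-8) to the listed intervals. The LLN values are assumptions.

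| Count | LLN 1.5 | LLN 1.8 | LLN 2.0 |
|---|---|---|---|
| 0.3 | level 1 | level 1 | level 1 |
| 0.7 | level 2 | level 2 | level 2 |
| 1.2 | level 3 | level 3 | level 3 |
| 1.6 | none | level 4 | level 4 |
| 1.9 | none | none | level 4 |
| 2.5 | none | none | none |
| 4.5 | none | none | none |

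Every count at or above LLN falls in no level. If LLN is 1.5 or lower, the fourth level is empty as well. With a fifth level, ≥ LLN, each test count falls in exactly one level.

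**3. The other covariates.** The percentage definition (below 20% versus at least 20% drop) covers every patient with a baseline and a visit value, and its lower category is an unaffected reference. Baseline neutropenia is yes/no. Neither has the gap.

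**4. How many patients would be unclassified?** Planned arm sizes come from Protocol 5.2, which gives about 2253 for each of 300 mg and 150 mg, and "2160 for the 50 mg group and 3333 for the placebo group". Total: 2253 + 2253 + 2160 + 3333 = 9999. The documents do not give the share p below LLN at Visit 3 or 4, so a range is assumed. Classified = 9999 × p; unclassified = 9999 × (1 − p). Missing samples are ignored.

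| p (assumed) | Classified | Unclassified |
|---|---|---|
| 1% | 100 | 9899 |
| 2.5% | 250 | 9749 |
| 5% | 500 | 9499 |
| 10% | 1000 | 8999 |
| 20% | 2000 | 7999 |

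At p = 2.5%, about 56, 56, 54 and 83 patients would remain on 300 mg, 150 mg, 50 mg and placebo.

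**5. How much falls before the sample?** Assume a constant first-infection hazard h of 0.1 to 0.5 per year (not in the documents). The proportion of patients infected before time t is 1 − exp(−h·t).

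| h per year | Before Month 1.5 (t = 0.125) | Before Month 3 (t = 0.25) |
|---|---|---|
| 0.1 | 1.2% | 2.5% |
| 0.3 | 3.7% | 7.2% |
| 0.5 | 6.1% | 11.8% |

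As a share of all first infections over follow-up F, this is [1 − exp(−h·t)] / [1 − exp(−h·F)]. With F = 3.7 years (also an assumption) it is 4.0% to 7.2% before Visit 3 and 8.0% to 13.9% before Visit 4. Taking F from 3 to 5 years widens these to 3.2%–7.8% and 6.3%–15.1%.

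**The case against.** The strongest reply is that this is an omitted label. The four intervals have the same cut-points as CTC grades 4 to 1 in SAP Table 7-8, where an ungraded count is simply normal, and the platelet row in the same table shows the intended pattern. The SAP introduction says dataset specifications will follow, so a programmer might well add the level. That is plausible, and no passage says that normal counts are to be discarded. But SAP 2.2 lists these subgroups so that they are built into the analysis datasets, and the only definition given there is incomplete. The complete platelet row is no help in practice, since SAP 7.4.4 has no early-drop analysis.

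A reader might infer that the SAP's whole assessment of neutropenia and infection loses almost all patients. The documents do not support that. Two of the four early-drop models are affected. The percentage-change models, the baseline-neutropenia model in SAP 7.4.5 and the low-baseline-neutrophil subgroup in SAP 7.4.1 (Table 7-5) also address the link and classify patients fully. Nor is there any documented figure for the proportion lost. It is also not stated that the ordinal variable enters as a four-level class factor, so no claim about the number of interaction terms is made here.

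On timing, the reply is that SAP 7.4.5 is merely silent, and that a time-dependent covariate would be an alternative to a landmark. Both are fair. Yet the general rules in SAP 7.2 and 7.3.1 would then apply by default, and they count from randomization.

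**Conclusion.** The concern holds in limited form. The absence of a normal-count level is read directly from the table and needs no assumption; it leaves two of the four early-drop models without an unaffected reference group. That 80% to 99% of patients would be unclassified rests on an assumed 1% to 20% below LLN and on programming the row literally.

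The timing gap affects all four early-drop models. Its size rests on assumed hazards and follow-up: with F = 3.7 years, roughly 4% to 7% of first infections would precede Visit 3 and 8% to 14% would precede Visit 4.

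SAP 7.4.5 presents the analysis as exploratory, and SAP 7.1 makes no multiplicity adjustment for safety. The primary and key secondary analyses and the main infection tables are untouched. The correction is still worth making, because otherwise the reference group and time origin are left to be settled at programming.

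**What to change.** 1. In SAP Table 2.3-3, add ≥ LLN as the fifth level of the ordinal neutrophil variable and name it as the reference. State the unit, and say how the fourth level is handled if the laboratory's LLN is 1.5 × 10⁹/L or lower.
2. In SAP 7.4.5, start follow-up for the Visit 3 and Visit 4 models at the sample date, among patients still in follow-up with a count at that visit. Count only the first infection after that date. Add a sensitivity analysis excluding patients who had an infection before the sample.

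The cost is one table level and a few sentences. Infections before the landmark leave these exploratory models only. The number of main early-drop models stays at four, and no data collection changes.
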